#### **For the secondary objective**

The occurrence of pressure ulcer will be documented in data collection then calculated.

### **Research Design:**

- Open label randomized control clinical trial study with a pilot study-using questionnaire.

### **Inclusion Criteria:**

- Subjects  $\geq 18$ .
- Willing to participate.
- Patients undergoing cardiac surgery.
- Patient who is at risk for PU development as measured with Braden scale.

- 4 -

Title: Effectiveness of polyurethane foam (pink pad) compared with Mepilex dressing for pressure ulcer prevention in operating room

Version: 2.0 (20-Jun-2023)

Effective date: 15-Aug-2023

Expiration date: 15-Aug-2024

اللجنة المحلية لأخلاقيات البحث  
Institutional Review Board

## **Effectiveness of polyurethane foam dressing compared with Mepilex dressing for pressure ulcer prevention in operating room: A randomized control clinical trial.**

- Patient who has skin intact and having a life expectancy greater than 72 hours as per clinical judgement.

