## **Introduction**

The application of standard evidence-based prevention interventions can decrease the incidence of pressure injuries (PIs). However, the development of serious PIs in high-risk patients in the early postoperative period remains a significant clinical challenge. Following surgery, PIs that appear within 1 to 5 days are often deep-tissue pressure injuries (DTPIs) [1].

The etiology of DTPIs remains a topic of ongoing discussion among experts, and a comprehensive understanding of the underlying pathophysiological mechanisms has yet to be achieved. One commonly accepted hypothesis posits that the occurrence of DTPIs can be attributed to the application of pressure or shear stresses, or a combination thereof, resulting in cellular deformation and eventual necrosis. The DTPIs exhibit a distinctive complexity due to the co-occurrence of ischemia and mechanical stress, thereby expediting the consequent harm [2,3]

[figure not shown]
- 1 -

Title: Effectiveness of polyurethane foam (pink pad) compared with Mepilex dressing for pressure ulcer prevention in operating room

Version: 2.0 (20-Jun-2023)

Effective date: 15-Aug-2023

Expiration date: 15-Aug-2024

اللجنة المحلية لأخلاقيات البحث  
Institutional Review Board

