## **Effectiveness of polyurethane foam dressing compared with Mepilex dressing for pressure ulcer prevention in operating room: A randomized control clinical trial.**

DTPIs exhibit a discernible pattern of evolution. Initially, the affected area manifests abruptly as intact skin that exhibits discoloration, either in the form of purple or hyperpigmentation [2]. The lesions evolve into slender vesicles atop a dusky ulceration site, transforming into black eschar. Subsequently, the DTPI becomes unsealed, exposing a pressure injury that has penetrated through the entire thickness of the skin and underlying tissues, indicating a stage 3 or 4 injury [3,4]. According to a study conducted in 2013, it has been observed that wounds of this nature have the potential to heal without any loss of tissue. Nevertheless, it is imperative to provide sustained care and attention to prevent any deterioration [5].

Patients undergoing cardiac surgery are among those at the highest risk of developing PIs, with an incidence as high as 29.5% [6]. Among patients undergoing cardiac surgery, specific risk factors for PI include protracted exposure to pressure during lengthy surgical procedures, vascular disease, and/or postoperative vasopressor use [7]. The high incidence of PI among cardiac surgery patients suggests that conventional methods for preventing PI are inadequate for this population.

There are an increasing number of studies evaluating the efficacy of different dressings (typically multilayer foam dressings) in preventing pressure ulcers (PIs) of the sacrum, heel, and those related to medical devices in ICU and trauma patient populations [8,9]. Recent high-quality randomized controlled trials demonstrated that the use of specialty foam dressings over the sacrum can reduce the incidence of pressure ulcers in intensive care unit (ICU) patients and high-risk nursing home residents [10,11].

Although limited in design and/or sample size, additional research and quality improvement investigations support the efficacy of this intervention in preventing the formation of PIs [12]. The National Pressure Ulcer Advisory Panel, in collaboration with European and Pan-Pacific peer organizations, added a recommendation (with a "B" strength of evidence) to "consider applying a

[figure not shown]
- 2 -

Title: Effectiveness of polyurethane foam (pink pad) compared with Mepilex dressing for pressure ulcer prevention in operating room

Version: 2.0 (20-Jun-2023)

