### **Objective measures**

#### **For the primary objective**

Pressure ulcer incidence will be assessed by using Bates–Jensen Wound Assessment Tool (BWAT) after operation then day 3 and day 7 for both treatments.

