### **Exclusion Criteria:**

- Subjects under 18
- Not consenting to participate
- Patients with suspected hypersensitivity reactions to any of the dressing formulation's ingredients.
- Patients who are unable to continue the study because of death or change in the care setting.

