## **Effectiveness of polyurethane foam dressing compared with Mepilex dressing for pressure ulcer prevention in operating room: A randomized control clinical trial.**

There are two types of intervention available in King Abdullah medical city for operating room pressure ulcer prevention. **Polyurethane foams** (Pink Pad) are a single use system for use in surgical procedures. The system consists of a proprietary formulation for the pink foam pad, non-woven lift sheet, body straps, head rests, and boot liners. It aids hospital facilities in providing a safe and effective method of management of the patient for pressure ulcers and non-movement for patients in the Trendelenburg position.

**Mepilex Border Sacrum** dressings are self-adherent, multilayer foam dressings designed for use on sacrum aiming to prevent pressure ulcers. The dressings are used in addition to standard care protocols for pressure ulcer prevention.

After getting official permission from KAMC IRB, the subject will be randomized using electronic randomization 1:1 ratio. The randomization list was generated electronically through R using the Random Allocation Rule. Patients will equally be allocated into 2 groups randomly. The polyurethane foam group and Mepilex Border Sacrum dressings group.

**Standard PUs preventive care** - All included patients received standard PU prevention according to hospital protocols, based on contextualization and adaptation of International guidelines ( European Pressure Ulcer Advisory Panel, 2021 ), which involved: assessment of PU risk through the Braden Scale at hospital admission, every seven days and when clinically indicated (for example after surgery); full skin assessment during every shift, three times per day combined with routine positioning every 2 h or when required; use of active support surfaces (higher- specification foam mattress or dynamic anti-decubitus mattress) in case of Braden < 16, aiming at preventing damaging tissue deformation and providing an environment that enhances perfusion of at risk tissues; incontinence skin care.

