## **Effectiveness of polyurethane foam dressing compared with Mepilex dressing for pressure ulcer prevention in operating room: A randomized control clinical trial.**

Prior to surgery, Mepilex Border Sacrum dressings 20 X 20 (Molnlycke Health Care) will be applied to the patient's sacrum for Mepilex Border Sacrum dressings group and polyurethane foam will be used to the patient's sacrum for polyurethane foam group. A nurse in the preoperative patient receiving area will apply the Mepilex Border Sacrum dressings. The perioperative nurse will examine the dressing in the operating room to ensure its integrity. If the perioperative nurse observed any alterations to the original application, such as rolling or displacement, she will reapply it. If the dressing is not applied by the nurse before transferring the patient to the operation room the perioperative nurse will apply it. For polyurethane foam (pink Pad) it will be used only by operating room nurses as it is available only in the operating room. Both types of intervention will be available in the operating room.

Patient will be examined by head nurse of wound management team after the operation then at day 3- and 7-days post operation. The dressing should be removed after 7 days post operation or if there is any clinical indication for removal. If a patient is discharged before 7 days post operation for any reason the head nurse of wound management team will examine the patient before discharge. Follow up will be for maximum 7 days post operation for each subject. Any patient will be unable to continue the study because of death or change in the care setting will be excluded from the study.

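### Entry requires only intact skin, which does not rule out an existing deep-tissue injury, so a lesion present before surgery could be counted as incident

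*Protocol*

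**What the plan says.** **Eligibility.** The last item under Inclusion Criteria is "Patient who has skin intact and having a life expectancy greater than 72 hours as per clinical judgement". The other criterion related to pressure injury is "Patient who is at risk for PU development as measured with Braden scale", which grades risk and does not test for an existing lesion. Exclusion Criteria has four entries: age, lack of consent, "Patients with suspected hypersensitivity reactions to any of the dressing formulation's ingredients", and inability to continue through death or a change of care setting. None concerns an existing pressure injury, redness or discoloration.

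**The lesion expected.** The Introduction says that injuries appearing in the first 1 to 5 days after surgery are often deep-tissue injuries. It describes their onset: "Initially, the affected area manifests abruptly as intact skin that exhibits discoloration, either in the form of purple or hyperpigmentation".

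**Outcome assessment.** Objective measures states the primary measure as follows: "Pressure ulcer incidence will be assessed by using Bates–Jensen Wound Assessment Tool (BWAT) after operation then day 3 and day 7 for both treatments". Study Procedure adds: "Patient will be examined by head nurse of wound management team after the operation then at day 3- and 7-days post operation". For the secondary objective, occurrence of pressure ulcer is to be documented and calculated, with no further definition.

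**Data sheet.** Section I covers demographics, history, laboratory values and nutrition. Section II, the wound assessment, is completed only if a pressure ulcer occurs. Neither section has a baseline skin entry.

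**Standard care.** All included patients receive "full skin assessment during every shift, three times per day combined with routine positioning every 2 h or when required". The protocol links these checks neither to eligibility nor to the definition of a case.

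**The concern.** By the protocol's own account, the injury it most expects early after surgery begins under unbroken skin. A criterion met by unbroken skin does not screen that lesion out. If a patient arrives with a discoloured but intact sacrum, the first scheduled study examination that could note it takes place after the operation.

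Both objectives rest on counting new injuries: the primary compares pressure ulcer incidence between the two products, and the secondary estimates post-operative incidence at the centre. A lesion already there when the product is applied could not have been prevented by either one. If it is counted, the incidence estimate rises and the ratio between arms moves towards 1. A later analysis plan could define an incident case more tightly, but it could not apply that definition without a baseline skin status in the trial data.

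**Working it through.** **Step 1: follow one patient through the text.** Take a patient with purple, unbroken sacral skin before surgery.

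- Inclusion Criteria: the intact-skin item is met on its face, and the Braden item may well be met too.
- Exclusion Criteria: none of the four entries applies.
- Study examinations: after operation, day 3 and day 7. None is preoperative.
- Data sheet: no baseline skin field. Section II opens once a pressure ulcer is seen.
- Counting rule: occurrence, with no condition that the site was clear beforehand.

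Nothing in this chain stops the patient from entering or the lesion from being counted.

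**Step 2: the protocol's own figure.** The only calculated figure is the minimal sample size of 79. It reproduces: n = Npq / [(d²/z²)(N−1) + pq] with N = 90, p = q = 0.5, d = 0.05, z = 2.576 gives 22.5 / (0.0335 + 0.25) = 79.36. It does not bear on this point.

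**Step 3: effect on the observed rates.** Inputs:

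- π, the share enrolled with an existing intact-skin injury. This is not in the documents; 1% to 10% is assumed.
- r₁ = 29.5%, which the Introduction cites as an upper figure for cardiac surgery.
- r₂ = 14.75%, half of r₁, assumed.
- 40 patients per arm (Sample Size calculation).

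If every existing lesion is counted, observed rate = π + (1 − π) × r. At 5%, for example: 0.05 + 0.95 × 0.295 = 0.330 and 0.05 + 0.95 × 0.1475 = 0.190.

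| π (assumed) | Expected cases in 80 | Observed rates | Ratio (true 0.50) | Difference (true 14.75 points) |
|---|---|---|---|---|
| 1% | 0.8 | 30.2% vs 15.6% | 0.52 | 14.6 |
| 2.5% | 2 | 31.3% vs 16.9% | 0.54 | 14.4 |
| 5% | 4 | 33.0% vs 19.0% | 0.58 | 14.0 |
| 10% | 8 | 36.6% vs 23.3% | 0.64 | 13.3 |

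The chance of at least one such patient among 80 is 1 − (1 − π)⁸⁰: 55% at 1% and 98% at 5%.

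**Step 4: sensitivity to the comparator rate.** With 10% in place of 14.75%, the true ratio of 0.34 becomes 0.36, 0.44 and 0.52 at π = 1%, 5% and 10%. Normal-approximation power with 40 per arm (two-sided 0.05) falls from 59% to 57%, 49% and 42%. The direction is the same.

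**Step 5: chance imbalance.** Suppose exactly four of the 80 have an existing lesion. Under a 40/40 allocation, the probability that all four fall in one arm is 2 × (40×39×38×37) / (80×79×78×77) = 0.116. Some of these patients would have become cases anyway, so the expected net shift is 4 × (1 − 0.295) / 40 = 7.1 points or 4 × (1 − 0.1475) / 40 = 8.5 points, depending on the arm.

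**The case against.** The strongest reply is that the criterion is being read uncharitably. In a prevention trial, intact skin listed beside risk of developing a pressure ulcer is naturally meant as no existing injury. The research nurses are said to be trained in classifying pressure ulcers, and the word incidence ordinarily means new lesions. Standard care also includes a full skin check every shift, so a visible sacral discoloration may already be in the clinical record.

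Much of this stands. A reader might infer that the protocol compels sites to enrol injured patients and directs that their lesions be counted. It does neither: no sentence instructs an assessor to count a known existing lesion. The supportable statement is that such a patient can be enrolled and could be counted. What the reply does not remove is the gap itself. The Introduction distinguishes intact skin from uninjured skin, and the shift checks are connected to neither eligibility nor outcome.

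The size is also open to challenge. The documents contain nothing to suggest that such lesions are common before cardiac surgery, and at 1% the ratio barely moves. Randomisation balances them between arms on average. A reader might take each existing lesion to add a full 2.5 points (1 in 40) to its arm, and four in one arm to create a 10-point difference. Those are maxima: at the rates used, the expected net is about 1.8 to 2.1 points per lesion and 7.1 to 8.5 points for four.

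Finally, a reader might suspect that an unblinded assessor would reclassify early lesions as already present. The study is open label, including the outcome assessor, but the protocol provides for no such reclassification, so this is conjecture.

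**Conclusion.** The point holds as a gap in the wording and in the recorded data. It does not show that existing lesions will be counted. The criterion, read against the protocol's own description of deep-tissue injury, leaves room for an existing lesion to enter both incidence measures, and the planned data would not identify it.

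The main consequences are inflated incidence and dilution of the comparison; chance imbalance between arms of 40 is secondary. The effect on the ratio ranges from negligible at 1% prevalence to material at 10%. It rests on three assumptions: the prevalence, the halved comparator rate, and that every existing lesion is counted. The change is worth making because it is cheap and because baseline status cannot be reconstructed from trial data that never held it.

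**What to change.** - In Inclusion Criteria, replace the intact-skin wording with: *no pressure injury of any stage, including intact discoloured skin, at the last documented skin assessment before the envelope is opened*. The life-expectancy part of that item is unaffected.
- Add a short baseline skin entry to the data collection sheet, by body site, taken from the skin checks already made under standard preventive care.
- Under Objective measures, define an incident case as a lesion at a site recorded as clear at that assessment, and apply the definition to both objectives.

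**Cost.** No new procedure is needed. A few patients with early discoloration become ineligible, and the data sheet gains a site-level baseline entry with a matching rule for counting lesions. If the authors already meant intact skin as no existing injury, the rewording only states their intent.

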### **Exclusion Criteria:**

- Subjects under 18
- Not consenting to participate
- Patients with suspected hypersensitivity reactions to any of the dressing formulation's ingredients.
- Patients who are unable to continue the study because of death or change in the care setting.

### **Randomization**

Electronic randomization will be used as a simple technique of randomization. The randomization list was generated electronically using R and the Random Allocation Rule by a member of the research center who was not actively involved in the trial's enrollment and recruitment. A member of the research center will identify the participant for this concealment. To determine which treatment a participant will receive, an allocation sequence and envelopes containing the sequence will be generated. Each envelope will not be opened until the patient has consented and been enrolled in the study.

### **Blinding**

Open label study as True blinding for patients and the research nurse who will apply the dressing and Polyurethane foams (Pink Pad) will be difficult as there is a significant difference between the two treatment methods in presentation. Moreover, the skin imprint after the foam removal made it impossible to blind the outcome assessor.

### **Study Procedure:**

[figure not shown]
- 5 -

Title: Effectiveness of polyurethane foam (pink pad) compared with Mepilex dressing for pressure ulcer prevention in operating room

Version: 2.0 (20-Jun-2023)

Effective date: 15-Aug-2023

Expiration date: 15-Aug-2024

اللجنة المحلية لأخلاقيات البحث  
Institutional Review Board

## **Effectiveness of polyurethane foam dressing compared with Mepilex dressing for pressure ulcer prevention in operating room: A randomized control clinical trial.**

There are two types of intervention available in King Abdullah medical city for operating room pressure ulcer prevention. **Polyurethane foams** (Pink Pad) are a single use system for use in surgical procedures. The system consists of a proprietary formulation for the pink foam pad, non-woven lift sheet, body straps, head rests, and boot liners. It aids hospital facilities in providing a safe and effective method of management of the patient for pressure ulcers and non-movement for patients in the Trendelenburg position.

**Mepilex Border Sacrum** dressings are self-adherent, multilayer foam dressings designed for use on sacrum aiming to prevent pressure ulcers. The dressings are used in addition to standard care protocols for pressure ulcer prevention.

After getting official permission from KAMC IRB, the subject will be randomized using electronic randomization 1:1 ratio. The randomization list was generated electronically through R using the Random Allocation Rule. Patients will equally be allocated into 2 groups randomly. The polyurethane foam group and Mepilex Border Sacrum dressings group.

**Standard PUs preventive care** - All included patients received standard PU prevention according to hospital protocols, based on contextualization and adaptation of International guidelines ( European Pressure Ulcer Advisory Panel, 2021 ), which involved: assessment of PU risk through the Braden Scale at hospital admission, every seven days and when clinically indicated (for example after surgery); full skin assessment during every shift, three times per day combined with routine positioning every 2 h or when required; use of active support surfaces (higher- specification foam mattress or dynamic anti-decubitus mattress) in case of Braden < 16, aiming at preventing damaging tissue deformation and providing an environment that enhances perfusion of at risk tissues; incontinence skin care.

## **Effectiveness of polyurethane foam dressing compared with Mepilex dressing for pressure ulcer prevention in operating room: A randomized control clinical trial.**

Prior to surgery, Mepilex Border Sacrum dressings 20 X 20 (Molnlycke Health Care) will be applied to the patient's sacrum for Mepilex Border Sacrum dressings group and polyurethane foam will be used to the patient's sacrum for polyurethane foam group. A nurse in the preoperative patient receiving area will apply the Mepilex Border Sacrum dressings. The perioperative nurse will examine the dressing in the operating room to ensure its integrity. If the perioperative nurse observed any alterations to the original application, such as rolling or displacement, she will reapply it. If the dressing is not applied by the nurse before transferring the patient to the operation room the perioperative nurse will apply it. For polyurethane foam (pink Pad) it will be used only by operating room nurses as it is available only in the operating room. Both types of intervention will be available in the operating room.

Patient will be examined by head nurse of wound management team after the operation then at day 3- and 7-days post operation. The dressing should be removed after 7 days post operation or if there is any clinical indication for removal. If a patient is discharged before 7 days post operation for any reason the head nurse of wound management team will examine the patient before discharge. Follow up will be for maximum 7 days post operation for each subject. Any patient will be unable to continue the study because of death or change in the care setting will be excluded from the study.

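### The question is worded as operating-room prevention, but the arms also differ in device wear for up to 7 days after surgery

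*Protocol*

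**What the plan says.** **The question.** The title and the last sentence of the Introduction describe prevention in the operating room. Study Procedure opens the same way: "There are two types of intervention available in King Abdullah medical city for operating room pressure ulcer prevention". The primary objective under OBJECTIVES is softer, since its reference to the operating room may only say who the patients are.

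**The pad.** Study Procedure says that the pads "are a single use system for use in surgical procedures", and later: "For polyurethane foam (pink Pad) it will be used only by operating room nurses as it is available only in the operating room".

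**The dressing.** "A nurse in the preoperative patient receiving area will apply the Mepilex Border Sacrum dressings". The perioperative nurse checks it in the operating room and reapplies it if it has moved. Then: "The dressing should be removed after 7 days post operation or if there is any clinical indication for removal". The Setting section covers the operating room, the cardiac intensive care unit and the ward.

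**Other care.** "All included patients received standard PU prevention according to hospital protocols". The items listed are Braden scoring, skin checks each shift, two-hourly repositioning, active support surfaces when the Braden score is below 16, and incontinence care. No sacral dressing is among them. Of the trial dressing the protocol says: "The dressings are used in addition to standard care protocols for pressure ulcer prevention".

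**The outcome.** Objective measures and Study Procedure set examinations after the operation, at day 3 and at day 7. Patients discharged earlier are examined before they leave.

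**The concern.** An operating-room question calls for arms that differ in what protects the sacrum during surgery and are otherwise handled alike. Here one product appears to stop at the operating-room door, while the other stays on through intensive care and the ward. Two of the three examinations follow days in which only one arm is expected to have a study device.

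Under the present wording, a day-7 result favouring the dressing could be reported as better protection during surgery when some or all of it came from wear afterwards. A null result could hide a pad that does better during surgery but is offset by the dressing's later wear. Either reading could misdirect a decision about what to use in the operating room. Nothing in the protocol limits the attribution.

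**Working it through.** The protocol gives no figure on this point, and its sample size calculation does not bear on it. The check is therefore a comparison of sections.

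**Step 1. Study-device cover by interval**

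| Interval | Pad arm | Dressing arm |
|---|---|---|
| Before surgery | None; pad available only in the operating room | Dressing on (or applied in the operating room if missed) |
| During surgery | Pad | Dressing |
| End of surgery to day 3 | None, by inference | Dressing, unless removed on clinical indication |
| Day 3 to day 7 | None, by inference | Dressing, with the same exception |

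Outcomes are read at the end of the second, third and fourth rows. Only the immediate post-operative examination largely escapes the difference in post-operative wear.

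**Step 2. How firm is the inference of no cover?** It rests on the pad being a single-use surgical product, on its being available only in the operating room, and on the standard-care list naming no sacral dressing. Against it, pad removal at the end of surgery is never stated. The Introduction also says that this centre's open-heart patients receive both products, without making clear whether that means one each or both together. The removal instruction speaks of the dressing. The running title calls the foam a dressing too, but Study Procedure uses that word for the sacral product and names the pad separately.

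**Step 3. Does the protocol give reason to expect post-operative wear to matter?** Yes. The Introduction cites trials showing that "the use of specialty foam dressings over the sacrum can reduce the incidence of pressure ulcers in intensive care unit (ICU) patients", and it lists vasopressor use after surgery among the risk factors. Risk continues after surgery, and a sacral dressing may act on it.

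**Step 4. The mechanism, with assumed inputs.** Suppose that both products protect equally during surgery. Let r be the pad arm's day-7 risk, f the share of that risk arising after surgery, and q the relative risk of that share under the dressing.

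- Dressing-arm risk = r(1 − f) + r·f·q
- Difference between arms = r·f·(1 − q)

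The Introduction gives 29.5% as a high incidence in cardiac surgery. Every other value here is an assumption: r down to 15%, f from 25% to 75%, q from 0.3 to 0.7.

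- Lowest: 0.15 × 0.25 × 0.3 = 0.011, or 1.1 points
- Middle: 0.295 × 0.5 × 0.5 = 0.074, or 29.5% against 22.1%
- Highest: 0.295 × 0.75 × 0.7 = 0.155, or 15.5 points

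If q = 1 the difference is zero. This shows that a day-7 difference can arise with no difference in operating-room protection. It does not estimate how large that difference would be in this trial.

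**The case against.** **The wording can be read more generously.** The primary objective may only name the patients. The secondary objective speaks of injury after surgery, and the examination days, the dressing removal time and the ward setting are all stated openly. No sentence says that a day-7 difference will be credited to protection during surgery. This has force: the schedule is visible to a careful reader. But the title, the closing aim of the Introduction and the opening of Study Procedure still state a narrower question than the arms can answer, and those are the lines a report would inherit.

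**The imbalance may be smaller than it looks.** If routine care puts a sacral dressing on pad-arm patients after surgery, the difference shrinks or disappears. No sentence prohibits this. The objection stands as a limit on confidence, although the standard-care list points the other way.

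**The immediate examination answers the operating-room question.** Only in part. The Introduction describes post-operative injuries appearing 1 to 5 days after surgery, so that examination may miss damage that shows later. Nothing makes it the primary time point.

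**Stronger readings that the protocol does not support.** A reader might infer that, because procedures are expected to last a little over 4 hours or more and the dressing may stay on for 7 days, nearly all of any benefit must come from post-operative wear. Hours are not risk. The Introduction names prolonged pressure in long operations as a risk factor, and repositioning and support surfaces are provided as standard care. A reader might also infer that the trial is confounded or invalid. It is not: allocation is randomised and the two strategies can be compared fairly.

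**Conclusion.** The point holds as a mismatch between the stated question and the comparison made. The arms are a pad used in surgery and a sacral dressing worn from before surgery for up to 7 days after it. Day-3 and day-7 differences therefore combine device effects during and after surgery, and the randomised contrast is valid only as a comparison of those two strategies.

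The difference in post-operative study-device cover is up to 7 days against, by inference, none. Early removal or discharge shortens the time observed under wear. The consequence for incidence cannot be derived from the protocol. The wear schedule of the dressing and the operating-room wording are clear from the text; confidence is medium on the pad arm's lack of post-operative cover. The point is worth correcting because the wording decides what the trial may conclude.

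**What to change.** Reword the title, the last sentence of the Introduction, the primary objective and the opening sentence of Study Procedure along these lines: *pad during surgery only versus sacral dressing from before surgery until removal (up to day 7), for pressure injury through day 7*. Add one sentence saying that day-3 and day-7 differences compare these two strategies and will not be attributed to operating-room protection alone. If pad-arm patients are in fact meant to have a sacral dressing after surgery, the new wording should say that instead.

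Wear time, examinations and sample size stay as they are. The cost is a narrower conclusion and, because the title and primary objective change, a probable ethics-board amendment for the wording.
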